Statistical Analysis Plan for DOD2: Can Early Initiation of Rehabilitation With Wearable Sensor Technology Improve Outcomes in mTBI?

NCT03479541

April 17, 2024

Statistical Analysis Plan

To evaluate differences in primary and secondary outcomes (all but Patient Global Impression of Change and Dynamic Visual Acuity), we used linear mixed-effect (LME) models with an intention-to-treat design. This statistical approach factors in the 6-week wait as well as the intervention time for the later physical therapy (PT) group, and allowed us to include data from all participants even those who withdrew or were lost to follow-up. Each LME model contained fixed effects for PT onset group (earlier or later PT), time since injury, and the group x time since injury interaction. The interaction effect examined the difference of change in the outcomes over time based on the group. The later PT group served as the reference. Both linear and quadratic time since injury were assessed in the model, and linear time was included in the final model. The full LME models also included apriori covariates of age, gender, and initial SCAT symptom severity total score, and random intercepts to account for within-participant correlations. Outcomes were assessed for normality assumptions in the LME models and were log transformed if necessary. We accounted for participants that withdrew or were lost to follow-up using inverse probability weighting in the model and sensitivity analyses were performed for inverse probability weights.

Primary Outcome

- 1) Dizziness Handicap Inventory (DHI)

Secondary Outcomes:

- 2) Neurobehavioral Symptom Inventory (NSI)
- 3) Quality of Life After Brain Injury (QOLIBRI)
- 4) Return to Activity Question
- 5) Vestibular/Ocular-Motor Screening (VOMS) Tool
- 6) Mini-Balance Evaluation Systems Test (Mini-BESTest)
- 7) Modified Balance Error Scoring System (mBESS)
- 8) Automated Neuropsychological Assessment Metrics (ANAM)
- 9) Instrumented Sway
- 10) Instrumented Walking
- 11) Complex Navigation Task
- 12) Central Sensorimotor Integration (CSMI) Test
- 13) Auditory Processing

Other Pre-specified Outcomes

- 14) Post-concussion Symptom Scale From the Sport Concussion Assessment (SCAT) Tool Version 5
- 15) Insomnia Severity Index (ISI)
- 16) Head Impact Test (HIT) – 6

Statistical Analysis Plan for Patient Global Impression of Change (Secondary Outcome)

The Patient Global Impression of Change (PGIC) is an ordinal variable where participants rate their global assessment of change on a scale from 1 to 7. To test whether the group with Earlier PT had larger improvements in the PGIC than the Later PT group, we conducted a Mann-Whitney U test to assess group differences in PGIC scores.

Statistical Analysis Plan for Dynamic Visual Acuity (Secondary Outcome)

We used a linear mixed-effect (LME) model with an intention-to-treat design. The LME model contained fixed effects for PT onset group (earlier or later PT), time point (pre-PT or post-PT), and the group x time point interaction. The interaction effect examined the group difference of change in the outcomes between time points. The later PT group and pre-PT time point served as the references. The full LME model also included apriori covariates of age, gender, initial SCAT symptom severity total score, days since injury before starting PT, and random intercepts to account for within-participant correlations. Outcomes were assessed for normality assumptions in the LME models and were log transformed if necessary. We accounted for participants that withdrew or were lost to follow-up using inverse probability weighting in the model and sensitivity analyses were performed for inverse probability weights.

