We demonstrated the resolution of symptoms in very mild mTBI was associated with increased head rotation during walking with head turns (Fig. 6). Power analysis for the secondary outcome (head-turn velocity) was derived from our pilot data assessing improved head velocity over time. In an mTBI cohort, a significant rate of change was observed with increasing head-turn velocity over time ($N=26$, $t=4.07$, $p<0.001$, Cohen's $d=0.798$, Fig. 6). With the same sample size of 36 per group, a significant effect of early versus later intervention would still be observable at $\alpha=0.05$ with 80% power, if there is at least a 56% difference in the effect size ($d=0.446$) between the two time-course arms for either intervention group. Similarly, this effect size could also be observed to be statistically significant between the feedback-enhanced intervention and standard exercise regime within either the time to rehabilitation cohorts. Assuming a dropout rate of ~20% over the study period, the expected effects sizes would be found to be significant with a final recruitment of 40 subjects for each of the four groups; totaling 160 people with mTBI for aims I and II combined.

II combined.

Primary outcome: DHI The final sample for Aims I and II will consist of four distinct groups: A) early rehabilitation using wearable sensors at-home, B) early intervention with traditional at home exercise program, C) late rehabilitation using wearable sensors at-home, and D) late intervention with traditional at home exercise program. Linear mixed-effects models will be used in an intention-to-treat design to assess the continuous rate of change in DHI over time in each group. Mixed-effects models will be used to account for within-subject correlation in the repeated measurements across time while addressing any missing data due to dropouts or absentee visits. An on-treatment comparison will also be leveraged, using ordinary least squares to model to bulk change in study outcomes from baseline to study exit for all subjects completing the study.

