To compare the effect of early versus late intervention, the main effect of time (Aim I, comparing groups AB to CD) will be assessed in the mixed-effects model. To compare the effect of rehabilitation with home monitoring versus standard-of-care rehabilitation, the main effect of treatment will be assessed in the mixed-effects model (Aim II, comparing groups AC to BD). To compare whether the effect of at-home monitoring is different between early and late rehabilitation, the interaction between time and treatment will be evaluated using the mixed-effects model. Beyond the main effects of time, treatment and their interaction, individual contrasts among groups will be considered using an ANOVA framework to compliment mixed-effects regression model.

Mixed-effects models will also incorporate covariates found to influence study outcomes, including, but not limited to, age, gender, vestibular function. For the intention-to-treat mixed-effects models, an unstructured error covariance structure will be utilized and parameters will be estimated using restricted maximum likelihood procedures. Missing data points in the analytical sample are considered missing at random and the above approach is sufficient under this assumption. Results will be considered significant at $\alpha=0.05$ with Holm-Bonferroni adjustments to correct for multiple comparisons among the various outcome measures. Model fit and integrity will be examined using a combination of formal fit criteria and visual inspection of residual plots.

Secondary Outcome measures will be assessed using the mixed-effects models as described above to determine the effect of time and treatment on each outcome. To determine the meaningful change of head stability metrics after rehabilitation, the minimal detectable change of our novel outcome measures presented in Table 2 such as attenuation coefficient, cross-covariance of eye, head, and lumbar movements, peak axial rotational velocities, and sequential timing of reorientation will be calculated. Minimally clinically important difference for these novel measures will also be calculated using an anchor-based approach where clinically meaningful difference is based on PGIC.

9. Privacy, Confidentiality, and Data Security

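### The SAP carries only one of the protocol's three mixed-model contrasts: the sensor comparison and the timing-by-sensor interaction have no SAP analysis, and neither document says what became of them

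*SAP*

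**What the plan says.** **Protocol.** Section 2 (Objectives, Aim II) randomises participants in both timing arms a second time, to a home exercise programme with or without sensors. Comparing outcomes between those two groups is one of the aim's stated tasks. Section 8 (Data Analysis, Primary outcome) says: "The final sample for Aims I and II will consist of four distinct groups". They are early with sensors (A), early without (B), late with sensors (C) and late without (D). The mixed model is to be used "to assess the continuous rate of change in DHI over time in each group".

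The same section assigns three contrasts to that model:
- timing, AB against CD;
- sensor: "the main effect of treatment will be assessed in the mixed-effects model (Aim II, comparing groups AC to BD");
- timing by sensor: "the interaction between time and treatment will be evaluated using the mixed-effects model".

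It adds that "individual contrasts among groups will be considered using an ANOVA framework". The sample-size text also plans a sensor comparison, "between the feedback-enhanced intervention and standard exercise regime within either the time to rehabilitation cohorts".

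**SAP.** The main analysis covers 16 numbered outcomes, with the Dizziness Handicap Inventory (DHI) as primary: "Each LME model contained fixed effects for PT onset group (earlier or later PT), time since injury", with their interaction, age, gender, initial SCAT score and random intercepts. Patient Global Impression of Change (PGIC) gets a Mann-Whitney test of Earlier against Later PT. Dynamic Visual Acuity (DVA) gets a mixed model in PT onset group and time point. Sensors appear only in the SAP's title.

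**The concern.** Whether sensor-based home monitoring improves outcomes is one of the protocol's three objectives, and it rests on its own randomisation. An analyst who follows the SAP alone will produce no estimate of it and none of the interaction.

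Falling back on the protocol does not settle the matter, because its model and the SAP's differ. A sensor result reported later would have no clearly governing specification. If none is reported, readers cannot tell a planned change from an oversight.

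**Working it through.** No stated figure is at issue, so the first check sets the two documents side by side.

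| Protocol contrast | SAP main model | SAP PGIC | SAP DVA |
|---|---|---|---|
| Timing (AB vs CD) | yes, as a difference in slope | yes | yes, by time point |
| Sensor (AC vs BD) | no | no | no |
| Timing by sensor | no | no | no |

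So 3 − 1 = 2 protocol contrasts lack an SAP analysis, and 0 of 3 SAP analyses contain sensor assignment. The within-cohort sensor comparison in the sample-size text is absent too.

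**The interactions are not the same.** In the protocol's contrasts, time means early against late and treatment means home monitoring. The SAP's interaction is PT onset group by time since injury. It is part of the timing question and says nothing about sensors.

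**The models differ.** The protocol specifies an unstructured covariance fitted by restricted maximum likelihood, with covariates that include vestibular function. The SAP has random intercepts, inverse probability weighting, linear time since injury, and age, gender and initial SCAT score as covariates.

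**Adding a sensor-by-time term to the SAP's main model is not enough.** Illustration with assumed visit weeks, built from the 6-week wait (SAP), 6 weeks of PT and a follow-up 6 months later (protocol section 6; 6 months taken as 26 weeks):
- Early arm: weeks 0, 6, 32. Late arm: weeks 0, 6, 12, 38.
- Assume the same sensor effect in both arms: difference y = 0 before PT and 1 from post-PT onward.
- Slope b = Σ(t − t̄)y / Σ(t − t̄)², with complete data.

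Early: t̄ = 38/3 = 12.67. Denominator 0 + 36 + 1024 − 38²/3 = 578.67. Numerator (6 + 32) − 2 × 12.67 = 12.67. b = 12.67/578.67 = 0.0219 per week.

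Late: t̄ = 56/4 = 14. Denominator 0 + 36 + 144 + 1444 − 56²/4 = 840. Numerator (12 + 38) − 2 × 14 = 22. b = 22/840 = 0.0262 per week.

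The late slope is 0.0262/0.0219 = 1.20 times the early one, although the sensor effect is identical. Moving the origin from enrolment to injury by the same amount for everyone leaves both slopes unchanged. If the late arm starts at its pre-PT visit, its times are 0, 6, 32 from the start of PT, and both slopes are 0.0219.

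**The case against.** The strongest reply is that the protocol still provides a method. Its Data Analysis section assigns both missing contrasts to an intention-to-treat mixed model, with a covariance structure, an estimation method and a significance level, and nothing says that the SAP replaces it. This stands. A reader might infer that the sensor comparison has no planned analysis anywhere, or that Aim II was abandoned or withheld. The documents support neither: the gap is in the SAP, and Aim II may be analysed under the protocol or in a plan not supplied here. What remains is that neither document says so, and the two models disagree on points that the sensor contrast needs.

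A second reply is that the primary timing result is unharmed. This also stands, with a condition. A reader might infer that leaving out the sensor factor biases the timing comparison. With sensor allocation balanced within timing arms, as the planned 40 per group implies, it does not. Aim II's algorithm-validation and report-development tasks are unaffected too.

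A third reply is that not every possible sensor test was planned. For secondary outcomes the protocol names effects of time and treatment and otherwise refers back to the DHI model. In its analysis section PGIC serves only as the anchor for meaningful change. This limits what an addendum may call prespecified.

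**Conclusion.** The point holds as a gap between protocol and SAP. Two of three mixed-model contrasts, including the only one that answers Aim II's randomised question, have no SAP analysis, and their status is not stated. That is more than missing detail, because the SAP followed alone leaves a stated randomised objective unanswered.

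The conclusion rests on the term-by-term reading above and on there being no further plan among the documents supplied. The finding that the timing analysis is unbiased assumes balanced sensor allocation within timing arms. The 20% slope difference is illustrative: it depends on the assumed visit weeks and a step-shaped effect, and it bears on how to repair the gap, not on whether the gap exists.

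**What to change.** Leave the Aim I models unchanged. Issue a dated SAP addendum, disclosed as written after the April 2024 SAP:

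1. Confirm from the records when sensor allocation took place, and analyse everyone as allocated. The Aim II text suggests entry to rehabilitation, while section 6 (Intervention) describes a randomisation list for early against late only.
2. For DHI, then the other mixed-model outcomes, add sensor assignment with all lower-order terms. Estimate the sensor effect as change from the pre-PT visit to post-PT and follow-up, with time coded from the start of PT or as visit. The late arm's wait then stays out of the sensor slope. Section 6 already gives that arm a testing session just before PT.
3. Report the timing-by-sensor interaction as an estimate with a 95% confidence interval.
4. For DVA, add sensor, onset by sensor, sensor by time point and the three-way term.
5. For PGIC, compare sensor with no sensor only. Give no interaction unless an effect measure is named, since a Mann-Whitney test does not supply one.
6. Label as prespecified only the contrasts that the protocol names, and the rest as added.

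If Aim II was dropped or is analysed elsewhere, state that instead, with the reason or the location.

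**Cost.** No new visits or data, provided allocation and its date were recorded. The work is one further analysis for each of 18 listed outcomes (16 numbered, PGIC and DVA), and more where an instrument yields several measures. The alternative statement costs a sentence or two.

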Headache Impact Test- 6 (HIT-6): This questionnaire measures one's ability to function in everyday life (work, school, home and social situations). This questionnaire takes five minutes.

Quality of Life After Brain Injury (QOLIBRI): This questionnaire takes approximately 10 minutes and will ask them to rate your quality of life before and after concussion.

Concussion Symptom Subtype Inventory (CSSI): This questionnaire takes approximately 10 minutes and asks you to rate if you have had specific symptoms within eight categories at two points in time – before your injury and now.

Patients Global Impression of Change (PGIC): This single questionnaire takes approximately 1 minute and will ask people to rate how they perceive their health has changed over the course of treatment on a scale of 1-7.

Home monitoring: A subset of participants will be given an inertial sensor to wear at home for a period of time (i.e. 7 days) to follow their activity recovery at home.

Adaptation during COVID- 19 restrictions: Modified procedures during this time will be for study team members to ask questionnaires (listed above) over the phone or through a virtual visit. Participants will be emailed a PDF of the questionnaires for them to review while the study team member asks them to subjectively rate their symptoms.

Intervention: After participants are enrolled in the study, they will be randomly assigned to begin physical therapy immediately (approximately 2 weeks after their physician appointment) or within the standard of care timeline (approximately 8 weeks after their physician appointment). This randomization will be found on a pre-assigned list that was generated prior to their enrollment. This randomization will be performed in RedCap by a

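### The DHI slope on time since injury can miss an early benefit at about 6 weeks that the late arm later matches, so a null interaction does not rule one out

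*SAP*

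**What the plan says.** The SAP's model for DHI and most secondary outcomes has "fixed effects for PT onset group (earlier or later PT), time since injury, and the group x time since injury interaction", plus age, gender, initial SCAT score and random intercepts. It describes one effect as the comparison: "The interaction effect examined the difference of change in the outcomes over time based on the group". On the form of time it says "Both linear and quadratic time since injury were assessed in the model, and linear time was included in the final model". It gives neither the rule for that choice nor the scale (raw or log) on which it was made. It also claims that "This statistical approach factors in the 6-week wait as well as the intervention time for the later physical therapy (PT) group".

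The protocol (section 8, Primary outcome) planned mixed models "to assess the continuous rate of change in DHI over time in each group", so a slope is in line with it.

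The protocol (section 6, Intervention) starts PT "approximately 2 weeks after their physician appointment) or within the standard of care timeline (approximately 8 weeks after their physician appointment", and PT lasts 6 weeks. The post-PT visit follows each participant's own PT, and the last visit comes 6 months after that. Only the late arm has an additional session just before PT (section 5e on compensation; section 6, Aim I & II).

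**The concern.** A straight line fitted to each arm summarises the whole follow-up in one number. If PT lowers DHI by the same amount in both arms, only sooner in one, the arms differ for about 6 weeks and then agree. A slope over many months barely registers that, yet earlier relief is a large part of what Aim I asks. A null interaction could then be reported as no benefit of early PT.

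The visit days also differ between the arms. If recovery is curved, two arms on one identical curve can get different fitted slopes. The primary outcome and all but two of the secondary outcomes use this model.

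**Working it through.** **1. Visit times, in weeks after the physician visit (protocol, section 6).** Early arm: PT starts at about 2, so post-PT is at about 2 + 6 = 8, and the last visit 6 months later. Late arm: pre-PT at about 8, post-PT at about 8 + 6 = 14, and the last visit 6 months later. Early post-PT and late pre-PT nearly coincide. The late arm's post-PT and last visits fall about 6 weeks after the early arm's.

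**2. Noise-free slopes.** Assumed days since injury: 20, 66, 248 (early) and 20, 66, 108, 290 (late). Least-squares slope = Σ(t − mean t)·y / Σ(t − mean t)². The means are 111.3 and 121; the denominators are 29,074.7 and 41,956.

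*Same 10-point PT effect in both arms, flat otherwise.*
- Early (0, −10, −10): −10 × (−45.33 + 136.67) / 29,074.7 × 30 = −0.94 points per 30 days.
- Late (0, 0, −10, −10): −10 × (−13 + 169) / 41,956 × 30 = −1.12.
- At day 66 the early arm is 10 points better, yet the slope difference is +0.17, slightly towards late PT.

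*One identical curve, 30·exp(−t/200), no PT effect.*
- Early: −2,270.5 / 29,074.7 × 30 = −2.34.
- Late: −2,965.9 / 41,956 × 30 = −2.12.
- Difference −0.22, towards early PT.

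*Both together.* The two shifts oppose each other. An equal 5-point effect moves the difference from −0.22 to −0.14, and a 10-point effect to −0.05.

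*Log scale.* With log(DHI + 1) and a 30-point fall from day 20 (time constant 200 days), the early/late slope ratio drops from 1.10 (raw) to 1.01 with no plateau, or 1.05 with a 10-point plateau.

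**3. Simulation.** Assumptions not in the documents: SD (between/residual) 15/10 or 20/14 points; baseline at day 20 or spread over days 10-75; visits at +46/+228 (early) and +46/+88/+270 (late) days, ±7; the SAP's covariates; inverse probability weights; raw scale. Numbers are 80 per arm with 20% dropout, from the protocol's 160 and its dropout assumption. There were 3,000 trials per cell. Rates count only trials in which a common quadratic term was non-significant, so that linear time would be kept, and only cells with at least 200 such trials. The contrast is early minus late at about 6 weeks.

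| Truth | Slope favours early PT | 6-week contrast detects |
|---|---|---|
| 5 points, both arms | 1.2-9.8% | 36-64% |
| 7 points, both arms | 1.3-2.4% | 61-88% |
| 10 points, early arm only, lasting | 64-97% | 91-100% |
| 5 points, early arm only, lasting | 23-57% | 36-62% |
| 10 points early, late arm gains half | 17-24% | 90-100% |

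For 10 points in both arms, linear time is kept in only 0-15% of trials.

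*No PT effect, identical curved recovery (fall 20-40 points, time constant 120-300 days).* The slope rejects in 5.9-16.0% (30 cells, median about 9%), and 71-100% of those rejections favour early PT. The 6-week contrast rejects in 2.9-5.6%. With a straight course the slope rejects in 5.3-6.4%. The mean false slope difference is 0.08-0.37 points per 30 days; over the early arm's 228 days (7.6 × 30) that is about 0.6-2.8 points. A separate check of the same kind gave a lower conditional null rate, about 6-8%.

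**The case against.** The protocol chose a rate of change and the SAP follows it. Aim I includes long-term effects; if both arms end equal, a null slope is a fair answer to that question. The slope also detects a large lasting advantage. The 6-week contrast compares PT with waiting, which is a different question, and not estimating a quantity that the plan did not choose is not in itself an error. All of this stands, and it is why the slope model should stay.

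Three stronger readings are tempting, and the documents do not support them.

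- *That the model is biased towards early PT.* This needs convex recovery and no PT effect. It shrinks when both arms share a PT effect, shrinks in part on a log scale (which the SAP allows), and vanishes if the course is linear. The documents give no DHI curve or SD. Much higher false-positive rates arise only with strong curvature, where a quadratic check would seldom keep linear time.
- *That the slope will credit late PT.* The 10-point example shows the mechanism, but linear time would rarely be kept there.
- *That a planned 6-week contrast was dropped.* The protocol says "individual contrasts among groups will be considered using an ANOVA framework to compliment mixed-effects regression model". That names groups and no visit. Nor does the SAP say that no other contrast is reported.

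**Conclusion.** The point holds as a limit on what the interaction can show. A null DHI interaction does not exclude a benefit at about 6 weeks that the late arm later matches: for an assumed equal effect of 5 to 7 points, the slope favours early PT in about 1-10% of trials and a 6-week contrast detects the effect in about 36-88%. The mechanism follows from the visit schedule and the listed model terms; the sizes rest on the assumed SDs, visit days, dropout and p ≥ 0.05 rule for keeping linear time.

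The false-positive side is secondary and modest: roughly 6-16% against 5%, only for curved recovery without a PT effect, and without a reported log-scale simulation. The sentence about factoring in the wait claims more than the model does, because only the time axis reflects the wait. This is a cheap improvement that should be made; it does not invalidate the planned analysis.

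**What to change.** 1. Confirm that DHI was collected at the late arm's pre-PT visit. Protocol section 6 lists the questionnaires after the session that is repeated up to four times, which suggests so; the descriptions of the extra session in section 5e and under Aim I & II do not name DHI. Without it the contrast below cannot be done.
2. Keep the slope model. Beside it add, labelled post hoc, a mixed model with visit as a category (baseline, about 6 weeks, late post-PT, last visit) and baseline means constrained equal. Report the early-minus-late DHI difference at about 6 weeks (early post-PT v late pre-PT) with its confidence interval, described as PT versus waiting. Do not present it as a contrast that the protocol planned. Visit categories would also permit the protocol's intention that "an unstructured error covariance structure will be utilized".
3. State the rule and the scale used to choose linear over quadratic time.
4. Reword the sentence on the 6-week wait to say that only the time axis reflects it, and do not interpret a null interaction as no early benefit.
5. Show any long-term contrast at a common time as exploratory: the last visits are about 6 weeks apart, so it depends on interpolation.

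Cost: SAP wording and one extra model on data already collected, with no new visits. The downsides are a few more parameters, post hoc status, and only about 36-64% power for a 5-point effect.
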